9.3 Compliance

Analyses for compliance will be performed on subjects who received at least one dose of TMZ.

The frequency and percentage of subjects will be summarized by treatment arm for (1) at least 80% compliant of TMZ at every cycle in the investigator's opinion, (2) at least 80% compliant of TMZ at all but one cycle in the investigator's opinion, (3) less than 80% compliant of TMZ at more than one cycle in the investigator's opinion.

9.4 Protocol Deviations

The number and percentage of subjects with protocol specified eligibility deviations will be summarized by treatment arm assigned at the time of randomization, and split by type of deviation.

10.0 Efficacy Analysis

10.1 General Considerations

Unless otherwise specified, all efficacy analyses described below will be performed on the ITT population according to stratification factors based on the EORTC online randomization system (ORTA).

Time-to-event endpoints (TTE), such as overall survival and progression-free survival, are defined as the time from randomization to the first occurrence of the event. For subjects

who do not experience the event, TTE will be right-censored on the date of last adequate post-baseline assessment for that event. If a subject has no post-baseline assessment performed for the event (e.g., no imaging assessments for disease progression), then the data will be censored at the date of randomization. For each TTE endpoint, the corresponding event and the date of censoring are described in individual sections below.

All TTE will be computed in days and converted into months (1 month = 30.4375 days) for analysis, as follows:

$$\text{TTE} = (\text{date of event or censoring}) - \text{date of randomization} + 1) / 30.4375.$$

For the purposes of analysis, an event indicator will also be derived for each TTE for each subject, taking the value 1 if the subject is reported to have experienced the event or 0 otherwise.

Primary analysis of efficacy endpoints related to tumor assessments (e.g., ORR and PFS) will be based on assessments by a blinded, independent, central imaging review committee (IRC). For sensitivity analyses, these efficacy endpoints will also be analyzed based on assessments by local site investigators.

Tumor assessments will be based on the Response Assessment in Neuro-Oncology (RANO) criteria. Subjects for whom a complete response (CR) or partial response (PR) is observed, an additional MRI scan should be performed at least 4 weeks later to confirm the response. Any equivocal assessment of PD by the local investigator will need to be confirmed with an extra MRI performed at least 4 weeks later. If these subsequent evaluations suggest that the subject is in fact experiencing a CR, PR or PD, then the date of CR, PR or PD will be taken to be the date of the first such evaluation.

10.2 Efficacy Endpoints

The primary endpoint of this study is Overall Survival (OS), and the secondary endpoints are:

- PFS according to RANO criteria and assessed by IRC

- Objective response rate (ORR) assessed by IRC
- OS in the subgroup with EGFRvIII mutation

The following are exploratory endpoints:

- Best overall response rate (BRR), complete response rate (CRR), duration of response (DOR), and time to tumor response (TTR) assessed by IRC
- PFS in the subgroup with EGFRvIII mutation
- Neurological deterioration-free survival (NDFS)
- Quality of life
- Steroid use

Overall Survival (OS)

Overall survival (OS), or time to all-cause mortality, is defined as time from randomization to death due to any cause, regardless of whether the event occurred on or off study drug (ABT-414/TMZ/lomustine). For a subject who is not reported to have died at the time of data analysis, OS will be censored on the last documented date the subject is known to be alive.

Progression-Free Survival (PFS)

All disease progression assessed by IRC per RANO criteria will be included, regardless of whether the event occurred on or off study drug. Progression-free survival for a given subject will be defined as the time from the date of randomization till the date of first progression or the date of subject's death, whichever occurs first. If a subject neither experiences disease progression nor dies, then the subjects PFS will be censored at the last date of an adequate post-baseline tumor assessment.

Neurological Deterioration-Free Survival (NDFS)

Neurological deterioration (ND) is defined as a decrease in WHO performance status:

- for subjects with baseline WHO performance status 0 or 1: deterioration to WHO performance status 2 or worse for which no other explanation is present, and which is maintained for at least 3 weeks
- for subjects with baseline WHO performance status 2: deterioration to WHO performance status 3 or worse for which no other explanation is present and which is maintained for at least 3 weeks

NDFS will be measured as the time from randomization until first neurological deterioration or death whichever occurs first, regardless of whether radiological progression has occurred or not. If a subject neither experiences ND nor dies, then the subject's NDFS will be censored at the last date of post-baseline WHO performance status assessment.

Duration of Response (DOR)

The duration of overall response (DOR) will be analyzed only for the subset of subjects who experience a complete or partial response (CR or PR). For a given subject, DOR will be defined as the number of months from the day the criteria are met for CR or PR by IRC (whichever is recorded first) to the date of progressive disease or death, whichever comes first. If a subject is still responding (i.e., has not progressed nor died after CR or PR), then the subject's data will be censored at date of the last radiological assessment.

Time to Tumor Response (TTR)

Time to tumor response is defined as the time from the date of randomization to the observation of objective response (CR or PR).

For a subject who neither respond nor progress, TTR will be censored at the subject's last tumor assessment date. For subjects who progress and never respond, TTR will be set by convention as the longest time from randomization to the last tumor assessment observed across all subjects; i.e., $\max(\text{last tumor assessment date} - \text{randomization date} + 1)$ for all subjects. The distinction in censoring rule is made here since, at the time of censoring, the

former set of subjects would still have a possibility of experiencing a response (the event of interest), while the latter set of subjects never will.

Best Overall Response Rate (BRR)

Best overall response is the best response assessed by IRC from the date of randomization until disease progression or death, whichever comes first. Subjects who did not have post-baseline assessments will be considered "not-assessed." Subjects who had only one response that required a confirmatory MRI scan, which was not performed, will also be considered not-assessed.

Objective Response Rate (ORR)

Objective response includes best overall responses – complete response (CR) and partial response (PR) – assessed by IRC per RANO criteria from the date of randomization until disease progression or death, whichever comes first. All objective responses (CR and PR) must be confirmed by repeat MRI 4 weeks later than the first time when CR or PR is identified. Any subject who did not meet CR or PR including those who did not have post-baseline radiological assessments will be considered as non-responder.

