10.3 Efficacy Analyses

Statistical analyses will be performed to compare the primary and secondary endpoints described in Section 10.2 between each treatment arm (Arm 1 or Arm 2) and control (Arm 3) following the fixed sequence described in Section 4.6.

Analysis Methods for TTE Endpoints

For all TTE endpoints, differences between the treatment arms and the control arm will be assessed by a log-rank test stratified by the randomization stratification factors described in Section 4.3. The p-value obtained from the stratified log-rank test will be considered as the primary basis for determination of statistical significance for the TTE endpoints.

Kaplan-Meier (KM) estimates of the survival distribution of each TTE endpoint in Arms 1 – 3 will be estimated and plotted. Two-sided 95% CIs for the KM curves will be computed using Greenwood's formula and plotted. The median for the TTE and the probability of being event-free at 6 months, 1 year (12 months) and 2 years (24 months), and their 95% CIs will be estimated from the KM curve and its 95% CI for each treatment arm.

The hazard ratios of the two treatment arms over the control arm, adjusting for the main effects of randomization stratification factors as covariates, and their 95% CIs will be estimated using a Cox's proportional hazards model (score test).

The above-mentioned methods will be referred to as *primary survival analysis methods* for the remainder of this SAP. Analysis of the following endpoints will be performed using these primary survival analysis methods:

- Overall Survival (OS)
- Progression-Free Survival (PFS) assessed by IRC
- OS and PFS in subjects with EGFRvIII Mutation (in the Ev3M population)
- Neurological Deterioration-Free Survival (NDFS)
- OS and PFS in the subgroup of subjects with timing of relapse (< 16 weeks vs. \geq 16 weeks after the first day of the last TMZ cycle)
- Time to Tumor Response (TTR)
- Duration of Response among treatment responders (CR or PR). The time origin for calculating DOR is not the date of randomization.

Objective Response Rate (ORR)

The number and percentage of subjects with objective response will be presented by treatment arm. The objective response (CR and PR) rate will be reported with exact (binomial) two-sided 95% CI for each treatment arm.

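### As worded, the time-to-response rule censors patients who die without IRC progression as if they could still respond, which biases the estimated response probability slightly upward

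*SAP*

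**What the plan says.** SAP section 10.2 has two TTR rules for patients without a response.

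- No response and no progression: "For a subject who neither respond nor progress, TTR will be censored at the subject's last tumor assessment date".
- Progression and no response: "For subjects who progress and never respond, TTR will be set by convention as the longest time from randomization to the last tumor assessment", the maximum being taken over all subjects.

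The SAP justifies the difference by saying that the first group "would still have a possibility of experiencing a response" and the second group never will. Neither rule mentions death.

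The neighbouring definitions do. PFS is censored "If a subject neither experiences disease progression nor dies". A subject counts as still responding for duration of response if the subject "has not progressed nor died after CR or PR". Best overall response and objective response are also assessed up to progression or death.

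Under SAP section 10.1, if there is no post-baseline assessment for an endpoint, "then the data will be censored at the date of randomization". Section 10.3 lists TTR among the endpoints for the primary survival methods: a stratified log-rank test, a Cox model and "Kaplan-Meier (KM) estimates of the survival distribution of each TTE endpoint".

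The protocol's definition of progressive disease (section 7.1.1.4) adds that failing to come back for evaluation because of death or deterioration should count as progression.

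**The concern.** A patient who dies with neither a response nor an IRC-assessed progression meets the literal condition of the first rule. The reason given for that rule is untrue of this patient, and the reason given for the second rule fits exactly. If the death comes before any follow-up scan, section 10.1 censors the patient at randomization, so the patient never enters the risk set for a response.

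Two events end the chance of a response, and the rule treats them in opposite ways: progression keeps the patient at risk and death removes the patient. Removing patients before later responses makes every later step of the curve larger. The estimated response probability can then exceed the crude response rate, and the TTR log-rank and Cox results rest on a mixture of two ways of handling competing events.

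**Working it through.** The documents give no TTR figure to reproduce. The check computes 1-KM twice on the same data: (a) with deaths without progression or response censored at the last scan, or at day 1 if never scanned; (b) with the same patients held to the maximum time, as progressors are.

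**Inputs from the documents.** 240 patients randomized 1:1:1, so 80 per arm (protocol 8.1.1, SAP 4.2). Scans every 8 weeks (protocol 7.1.1.3). Median PFS 2.6 months for control and 4.8 months for ABT-414 (protocol 8.3). Median OS 7 and 12.9 months (protocol 8.1.1). 1 month = 30.4375 days (SAP 10.1).

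**Assumptions, not in the documents.** The response rate, the timing of responses, and the share of patients who die without IRC progression.

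**1. Worked example.** 80 patients; 12 respond (6, 4 and 2 at weeks 8, 16 and 24), a crude rate of 12/80 = 15.0%. Eight (10% of the arm) die without progression or response: 4 before week 8, 2 between weeks 8 and 16, and 2 between weeks 16 and 24. The rest progress.

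- Rule (a): the risk sets are 80 - 4 = 76, then 76 - 6 - 2 = 68, then 68 - 4 - 2 = 62. 1-KM = 1 - (70/76)(64/68)(60/62) = 16.1%.
- Rule (b): 1-KM = 1 - (74/80)(70/74)(68/70) = 15.0%, the crude rate.

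With 5% and 20% of the arm dying in this way (2/1/1 and 8/4/4 patients), rule (a) gives 15.5% and 17.4%. The excess grows roughly in proportion to the response rate: with 20 responders (10/6/4) and 20% such deaths, rule (a) gives 29.2% against 25.0%.

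**2. Simulation.** 1,000 replicates of 80 patients, exponential PFS at the design medians, and potential responses at weeks 8, 16 and 24 with weights 0.50, 0.35 and 0.15. A response counts only if it comes before the PFS event. The latent response rate is the rate before that condition is applied.

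| Arm (latent rate 30%) | Share of first PFS events that are deaths | Rule (a) | Rule (b) | Excess (points) |
|---|---|---|---|---|
| Control | 10% | 14.8% | 14.1% | 0.7 |
| Control | 20% | 15.7% | 14.3% | 1.5 |
| Control | 30% | 16.7% | 14.3% | 2.4 |
| ABT-414 | 10% | 20.3% | 19.7% | 0.7 |
| ABT-414 | 20% | 21.3% | 19.9% | 1.4 |
| ABT-414 | 30% | 22.0% | 19.8% | 2.2 |

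(The excess is taken before rounding.) At a latent rate of 10% the excess is at most 0.8 points. With no such deaths it is zero.

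**3. Limit from the design survival.** Suppose all responses come at week 8 and a fraction x of the arm has died unscanned before then. The risk set is N(1 - x), so 1-KM = response rate/(1 - x). Take x as all deaths expected by week 8 under exponential survival, with 8 weeks = 56/30.4375 = 1.84 months.

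- Control: x = 1 - exp(-ln 2 × 1.84/7) = 16.7%. A 15% rate reads as 0.15/0.833 = 18.0%.
- ABT-414: x = 1 - exp(-ln 2 × 1.84/12.9) = 9.4%. A 15% rate reads as 0.15/0.906 = 16.6%.

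**The case against.** The strongest reply is the clause in protocol section 7.1.1.4. Patients who deteriorate and die before a scan are the ones it describes, and SAP section 10.1 bases tumor assessment on RANO. If the clause is applied, they are progressors, take the maximum-time convention and are not censored at randomization. This narrows the gap but does not close it. The SAP does not cite the clause for TTR. TTR is assessed by the IRC, which reads MRI scans (protocol 15.5), and a patient who never returns gives it nothing to read. Both documents list death separately from progression in PFS.

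Two further points stand. First, the SAP reports event-free probabilities, so what is too high is 1-KM, and the plotted curve is too low. Second, censoring at a competing death is not in itself invalid: it targets the cause-specific hazard of response. The fair criticism is that progression is handled in one way and death in another. No distortion of the TTR test has been calculated, and the documents do not show which arm would gain.

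A reader might infer a much larger bias, for example a 15% response rate reading as 0.15/(1 - 0.30) = 21.4%. That needs 30% of an arm to be dead or otherwise lost, unscanned and without progression, before week 8. The design medians imply about 17% (control) and 9% (ABT-414) total deaths by then.

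**Conclusion.** The concern holds as a gap in wording with a small, one-directional effect. Read literally, the TTR rule censors patients who die without IRC progression, against its own stated reason, and 1-KM is at or above the value obtained when death is treated like progression. Over the simulated range (0-30% of first PFS events being such deaths, latent response rate 10-30%) the excess is about 0 to 2.4 percentage points. In the week-8 limiting case a 15% rate would read as about 18% (control) or 17% (ABT-414). These sizes are conditional, because the documents give neither the share of such deaths nor a response rate.

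A reader might also infer that the response results in the testing sequence are affected. They are not. ORR counts every patient without a confirmed response, including those never scanned, as a non-responder. TTR is exploratory, lies outside the fixed sequence, and is not performed by the EORTC (SAP section 12). No confirmatory result changes.

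**What to change.** In SAP section 10.2, extend the maximum-time rule to *subjects who progress or die and never respond*, and limit the censoring rule to subjects alive without progression or response at their last assessment. State that a patient who dies before any post-baseline scan falls under the maximum-time rule and not under the section 10.1 default. Then 1-KM matches the crude response rate, apart from patients who are alive and still unresolved at the cut-off. If the sponsor means the protocol 7.1.1.4 clause to govern TTR, the same edit should say so.

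The cost is a few words and one line of programming, with no new data. A cumulative incidence curve with progression and death as competing events is an optional alternative, but it would change the method set out in section 10.3.

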7.1 Evaluation of activity

7.1.1 General method of response assessment

Response to treatment is assessed on the basis of a set of target lesion(s) chosen before the first treatment administration (the complete list of target lesions must be reported on the initial measurement form before the start of treatment). These lesions must initially be measured in their two perpendicular dimensions, and these measurements must be repeated at each evaluation of the disease by the same method. Response evaluation is based on neuro-radiological imaging (MRI). For this protocol objective response (complete, partial response) and progression will be assessed by MRI (see section 7.1.1.4). Objective response will only be assessed in patients not having undergone second surgery with complete removal of contrast enhancing lesions prior to study entry. For these patients measurable disease is required, which is defined as a clearly enhancing tumor with at two perpendicular diameters at entry equal or superior to 1 cm.

The contrast enhancing area will be considered as the basis for the tumor size assessment. Tumor size is defined as the product of the two largest perpendicular diameters. For evaluating partial and complete response, the baseline scan must be used for initial comparison. In initially responding ($\geq 50\%$ reductions in cross-sectional areas) or stabilized ($< 50\%$ reduction and $< 25\%$ increase in cross-sectional areas) patients, new scans must be compared to the nadir, this is the scan showing the maximum response (i.e. minimum tumor size) during or after treatment. In assessing response, changes on T2 weighted images must be taken into consideration.

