- Stable Disease: This occurs if the patients did not qualify for complete response, partial response, or progression (see below) and requires: 1) No meaningful change in the appearance of the FLAIR/T2 images compared to baseline or to the nadir (point with the smallest FLAIR/T2 abnormalities) if a decrease occurred. 2) The patient should be stable clinically. In the event the steroid dosage has been increased for new signs and symptoms without confirmation of disease progression on imaging, and further follow-up imaging shows that with hindsight this increase in steroids was indeed unequivocally needed due to disease progression, the date of progression will be the date steroids were increased.
- In this protocol, although the primary endpoint is OS, in view of the relevance of objective responses, PR, CR, and equivocal PD need to be confirmed with an extra MRI made 4 weeks later.

Criterion	CR	PR	SD	PD
T1 gadolinium enhancing disease	None	≥ 50% ↓	<50% ↓ but <25% ↑	≥ 25% ↑
T2/FLAIR	Stable or ↓	Stable or ↓	Stable or ↓	↑
New lesion	None	None	None	Present
Corticosteroids	None	Stable or ↓	Stable or ↓	Not applicable*
Clinical status	Stable or ↑	Stable or ↑	Stable or ↑	↓
Requirements for response	All	All	All	Any

*increase in steroids alone does not qualify for PD

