7.1.3.1 Best overall response

Best overall response is the best response designation recorded from the date of randomization until disease progression.

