7.1.3.2 Objective response

Objective response includes best overall responses CR and PR. All responses must be confirmed by repeat MRI 4 weeks later.

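### SAP 10.2 puts patients whose only CR/PR was never re-scanned into the same not-assessed category as patients with no post-baseline scan

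*SAP*

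**What the plan says.** SAP 10.2, under Best Overall Response Rate (BRR), defines best overall response as the best IRC reading between randomization and progression or death. It then names two groups that become not-assessed. The first is patients without any post-baseline assessment. The second is given by this sentence: "Subjects who had only one response that required a confirmatory MRI scan, which was not performed, will also be considered not-assessed".

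The protocol defines the same quantity in 7.1.3.1: "Best overall response is the best response designation recorded from the date of randomization until disease progression". Section 7.1.3.2 adds, for objective response, "All responses must be confirmed by repeat MRI 4 weeks later", and 7.1.1.4 repeats the requirement: "PR, CR, and equivocal PD need to be confirmed with an extra MRI made 4 weeks later". Neither 7.1.1.4 nor 7.1.3.1 has a not-assessed category, and neither says how to class a CR or PR that was never confirmed.

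On timing, SAP 10.1 accepts a confirmatory scan taken four weeks or more after the first. MRI continues every 8 weeks until progression, on treatment and after it (Protocol 6.3.6, 6.4.1 and 7.1.1.3).

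BRR is exploratory (SAP 10.2). It is tabulated by category and arm (SAP 10.3), repeated on local investigator reads (SAP 10.5) and repeated by subgroup (SAP 10.6).

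**The concern.** A not-assessed line in a response table normally tells the reader how much imaging is missing. Here it would also hold patients who were imaged and whose scan was read as at least a 50% reduction. The two groups mean opposite things about the treatment, and the table as planned gives no way to separate them. An arm with more responses that were never re-scanned would appear to have more missing imaging.

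The rule also produces an odd ordering. A patient with 40% shrinkage on the only post-baseline scan is SD, if the other SD conditions are met. A patient with 55% shrinkage on the only scan, and no second scan, is grouped with patients never scanned. If the phrase about having only one response is read as one CR/PR rather than one assessment, a patient with SD at week 8 and an un-rescanned PR at week 16 also ends as not-assessed, below a patient who had SD alone.

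**Working it through.** The plan gives no figure to reproduce here. The check is a comparison of rules, followed by one line of arithmetic.

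**1. Where each provision puts a patient with an IRC-read CR/PR and no confirmatory scan**

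| Provision | Result |
|---|---|
| SAP 10.2, BRR definition | The patient has an IRC assessment, so some response category should apply |
| SAP 10.2, second not-assessed rule | Not-assessed |
| Protocol 7.1.3.1 | A designation is on record; read literally, this could even keep CR/PR |
| Protocol 7.1.3.2 | Not an objective response, because unconfirmed |
| Protocol 7.1.1.4, SD text | Possibly SD, as the residual category, if further conditions hold |
| Protocol 7.1.1.4 table and 7.1.1 | Not SD, because SD is limited to less than 50% reduction |

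The protocol provisions disagree among themselves, but none of them leads to not-assessed. Only the SAP sentence does, and it conflicts with the definition that opens its own paragraph.

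**2. Who is caught**

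The sentence applies only where the confirmatory MRI was not done. A response that was re-scanned and refuted is outside it. Under the timing in SAP 10.1, the next routine 8-week scan can serve as confirmation even if the extra 4-week scan was missed. The rule then reaches mainly patients whose first CR/PR was on their last scan, for example because of death, withdrawal or data cut-off.

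The group need not be empty. Protocol 15.5 has most central reads done in batches and without knowledge of the local read. A PR seen only by the IRC may therefore not prompt the site to order the extra scan.

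**3. Size**

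- Planned total: 240 (Protocol 8.1.1). Allocation: 1:1:1 (SAP 4.2). Per arm: 240 / 3 = 80.
- Shift in the not-assessed percentage for k such patients in an arm: 100 × k / 80 = 1.25 × k points. One patient gives 1.25 points and two give 2.5.
- k is not given in either document.

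**4. What does not move**

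SAP 10.2 counts anyone who did not meet CR or PR as a non-responder for ORR, including patients never imaged. Relabelling an unconfirmed CR/PR therefore changes ORR by 0 for every k, and likewise the complete response rate. OS, PFS and the hypotheses in SAP 4.6 do not use the BRR categories.

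**The case against.** The strongest reply is that the SAP is filling a gap the protocol left, and that sending unconfirmed responses to a neutral category is conservative. Part of this stands. A reader might infer that the protocol makes such a patient SD, so that the SAP simply contradicts it. The documents do not support that. The SD text reads "This occurs if the patients did not qualify for complete response, partial response, or progression (see below) and requires", and what follows are conditions on FLAIR/T2 appearance and clinical stability. The response table in 7.1.1.4 and the general method in 7.1.1 both limit SD to less than 50% reduction, and a scan that met CR or PR lies outside that limit. Residual wording and size limit point in different directions, and the protocol does not settle it.

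A reader might also infer that equivocal progression falls under the rule, so that an early progressor who dies before the extra scan is hidden as not-assessed. That does not hold either. SAP 10.1 ties confirmation of equivocal PD to the local investigator, whereas the main BRR is IRC-based. Protocol 7.1.1.4 counts failure to return because of death or deterioration as progression.

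It is also fair to say that the reference to only one response could mean patients whose sole post-baseline assessment was that scan. On that reading an earlier SD survives. The wording permits both readings, which is itself a reason to state the rule.

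Finally, the table is exploratory and carries no test. That limits the consequence but does not make the label correct.

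**Conclusion.** The point holds in a narrow form. SAP 10.2 labels scanned patients with an un-rescanned CR/PR as not-assessed. This conflicts with its own definition of best overall response and with Protocol 7.1.3.1, and as worded it can displace an earlier SD. It does not establish that these patients are SD, and it says nothing about responses that were re-scanned and not confirmed.

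The size is 1.25 percentage points per affected patient, assuming the planned 80 per arm. The documents give no basis for a total, nor for saying which arm would be affected more. The expectation that few patients are caught rests on the confirmation timing in SAP 10.1; if confirmation had to come from a scan at 4 weeks exactly, more would be. This is a minor presentation fault in exploratory tables and leaves the trial's primary and secondary conclusions untouched.

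**What to change.** Amend the BRR paragraph of SAP 10.2 in three respects:

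- Reserve not-assessed for patients with no adequate post-baseline scan.
- Add a separate line to the BRR tables for unconfirmed CR/PR with no confirmatory scan.
- Where an earlier assessment qualified as SD, keep SD as the best overall response and flag the unconfirmed CR/PR.

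This works whichever way the protocol's SD wording is read, because it does not force the unconfirmed scan itself into SD. Apply the same rule to the local-read and subgroup versions of the table (SAP 10.5 and 10.6). The cost is a few lines of SAP text, one derivation rule and one extra table row, with no new data collection.
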